5.6 Data Analysis

Sample Size and Power Calculations:

Provider Sample (Implementation Data; Aim 1)

No formal sample size calculations were used for the implementation-focused elements of this project. Rather, the team will invite all CBOC providers at all sites within the HOU and OKC VAMCs to participate and subsequently evaluate how many providers opted to engage in the bCBT project. These procedures are common for implementation-focused trials that often have a smaller pool of “subjects”. Designs of this nature often look less at statistical significance and

instead focus more on descriptive quantitative data and depth interviewing and qualitative analyses to determine impact and “lessons learned”.

Veteran Sample (Effectiveness Data; Aim 2)

Sample-size calculations indicate that 232 patients will need to be randomized to address the primary hypothesis for aim 2. Based upon our current project, we will need to recruit 300 Veterans. Approximately 30% of recruited participants were screened ineligible due to subthreshold anxiety and/or depression scores.

We will use unequal randomization to reduce unnecessary recruitment, resulting in 138 patients for bCBT and 94 for EUC. In determining the sample size, we first determined the number of participants needed to have 80% power to detect significant differences in the primary outcomes between our groups. We then inflated this to account for intraclass correlations among patients and for attrition and loss to follow-up. A sample size of 70 patients in both the bCBT and EUC groups (140 total) is needed to detect a difference in the means of the primary outcome that reflects a small effect size of .30, using a 2-sided *t*-test with 80% power at the .05 significance level, adjusted for repeated measures.⁵⁶ The small effect size was chosen to ensure an adequate sample size to address multiple study aims and outcomes. The bCBT sample size was then inflated by $[1 + (m - 1) c]$ to account for the intraclass correlation due to clustering of patients within bCBT clinicians.⁵⁷ Based on the sample size of 70 bCBT patients, an average of 5.8 patients per therapist, and an assumed correlation, *c*, among patients of .10,⁵⁷ our inflation factor is 1.48 ($70 \times 1.48 = 104$). A clustering inflation factor was not used for the EUC group. Both the bCBT and EUC groups are inflated to account for attrition rate at 12 months of 25%.

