Aim 2 will determine whether depression and quality of life outcomes differ as a function of the intervention at posttreatment, and at 8- and 12-month follow-ups. All analyses will be done on an intention-to-treat basis. Following the recommendation of the CONSORT group, we will not test for differences in baseline characteristics or adjust subsequent analyses for any variables we did not decide a priori to include in the regression models.⁶³ To compare changes between the 2 groups over time, we will use a longitudinal, mixed-model analysis containing terms for the intercept, treatment, time period and interaction between time and treatment. Separate models will be run for each outcome (PHQ-9, BDI, SF-12 PCS and MCS) and for the combined outcome of whether or not the patient responded to treatment as measured by both a 50% reduction in PHQ-9 and BDI-II. Linear regression will be run for the continuous outcomes and logistic regression will be used for the combined depression outcome. We will include the use of antidepressant medications, receipt of outpatient mental health care, the modality of treatment (e.g., telephone, in-person, combination), and the stratification variable, site, in the analyses to control for any possible differences that might exist between the treatment arms that might impact our outcomes. The interaction between time and treatment will indicate whether there is a difference over time between the 2 groups. We will conduct sensitivity analyses to evaluate whether the reasons for loss to follow-up at the various time periods are related to the observed values of the outcome variable, using tests for missing completely at random and tests for nonrandom missingness.⁵⁶

Analyses for Aim 2 will occur exclusively at the Houston HSR&D CoE under the direction of the PI ([name]), study statistician (Co-I [name]), and study data analyst ([name]).

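### The Aim 2 linear models do not pre-specify the baseline score as a covariate or say whether baseline is a time level, so precision is lost on either reading

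*Combined protocol and SAP*

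**What the plan says.** Under Analyses in Section 5.6, the Aim 2 outcomes are to be compared with a "longitudinal, mixed-model analysis containing terms for the intercept, treatment, time period and interaction between time and treatment". Separate models are run for PHQ-9, BDI, SF-12 PCS and SF-12 MCS, with a logistic model for combined response. Antidepressant use, outpatient mental health care, treatment modality and site are added. The plan says it will not "adjust subsequent analyses for any variables we did not decide a priori to include in the regression models". The time-by-treatment interaction is named as the term that shows whether the arms differ.

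The baseline score of the outcome is not among the terms, nor among the covariates described in Section 5.5. Table 3 and Section 6.0 show that it is collected: PHQ-9, BDI-II and SF-12 are all measured at baseline. Section 5.6 introduces the model as a comparison of change between arms, but it does not state whether baseline is a level of time. The outcome time points it names are post-treatment, 8 and 12 months.

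**The concern.** The baseline score is recorded before randomization on the same scale as the outcome, so it can be expected to predict follow-up. Conditioning on it is never less precise in a linear model in large samples, and it protects against chance imbalance. The plan can be read in two ways, and neither gets that benefit:

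- **Baseline as an unconstrained time level.** The interaction compares change from baseline between arms. The baseline data are used, but with a fixed coefficient of 1 where the data might support less.
- **Baseline left out.** The response is the 4-, 8- and 12-month values only. The baseline information is unused, and the interaction only asks whether the arm difference varies between visits.

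At stake is the width of the confidence intervals for the four continuous outcomes, and so the chance of detecting the effect of 0.30 for which the trial was sized.

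**Working it through.** **Inputs from Section 5.6.** The effect and test are given as a "small effect size of .30, using a 2-sided" test "with 80% power at the .05 significance level, adjusted for repeated measures". The base size is 70 per arm, the clustering factor 1.48 (bCBT arm only), and attrition 25%. Section 5.4 requires a baseline PHQ-9 of at least 10.

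**Assumptions (not in the documents).** The correlation ρ between any two measurements is 0.3, 0.5 or 0.7. The ratio k of baseline SD to follow-up SD is 1 or 0.8. The effect is equal at all three follow-ups, and there are 70 effective patients per arm.

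**Step 1: the plan's own figure.**
- bCBT: 70 × 1.48 = 103.6; 103.6 / 0.75 = 138.1.
- EUC: 70 / 0.75 = 93.3, taken as 94.
- Total: 138 + 94 = 232, as stated ("resulting in 138 patients for bCBT and 94 for EUC").

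The starting 70 is less transparent. A plain two-sample comparison needs 2 × [(1.960 + 0.842) / 0.30]² = 174.4, so 175 per arm. The repeated-measures adjustment must therefore supply a variance factor of 70 / 174.4 = 0.401. Under compound symmetry that factor arises from any of these:
- the mean of three follow-ups without baseline, at ρ = 0.10;
- change from baseline to that mean, at ρ = 0.70;
- a baseline-adjusted mean, at ρ = 0.54 (or 0.13).

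The 70 therefore does not reveal which analysis was intended.

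**Step 2: variance at one visit**, in units of the follow-up variance:
- follow-up only: 1
- change: 1 + k² − 2kρ
- baseline-adjusted: 1 − ρ²

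Adjustment saves ρ² against follow-up only and (k − ρ)² against change. Neither can be negative.

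| | ρ = 0.3 | ρ = 0.5 | ρ = 0.7 |
|---|---|---|---|
| Baseline-adjusted | 0.91 | 0.75 | 0.51 |
| Change, k = 1 | 1.40 | 1.00 | 0.60 |
| Change, k = 0.8 | 1.16 | 0.84 | 0.52 |
| Saving against follow-up only | 9% | 25% | 49% |
| Saving against change, k = 1 | 35% | 25% | 15% |
| Saving against change, k = 0.8 | 22% | 11% | 2% |

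Example at ρ = 0.5, k = 0.8: (0.8 − 0.5)² / 0.84 = 0.09 / 0.84 = 11%.

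**Step 3: what this does to power**, for the mean of three follow-ups. The variance factor V is (1 + 2ρ)/3 for follow-up only, that plus k² − 2kρ for change, and that minus ρ² for adjusted. Power is Φ(0.30 / √(2V/70) − 1.96).

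| | ρ = 0.3 | ρ = 0.5 | ρ = 0.7 |
|---|---|---|---|
| Follow-up only | 68% | 58.5% | 51% |
| Change, k = 1 | 45% | 58.5% | 80% |
| Change, k = 0.8 | 57% | 70% | 88% |
| Baseline-adjusted | 76% | 78.5% | 89% |

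**Step 4: the interaction test itself.** With baseline as an unconstrained level and k = 1, the joint 3-df interaction test has power 31, 42 and 65% at ρ = 0.3, 0.5 and 0.7. The joint 3-df test of the follow-up differences with baseline adjustment has 60, 63 and 77%. With follow-up visits only, a constant effect makes every interaction contrast zero, so power equals the 5% significance level.

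**The case against.** A reader might infer that the models throw away baseline data already collected and forbid their use. The documents do not support that. Section 5.6 frames the model as a comparison of change and rests on the interaction, which makes sense only if baseline is a time level; on that reading the scores are in the model. The bar on later adjustment is a general guard against post hoc covariate choice. It does not single out baseline, and it does not prevent an amendment before analysis.

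Four further objections carry weight:
- **Entry cutoff.** Requiring a PHQ-9 of 10 or more may make the baseline SD smaller than the follow-up SD. The saving against change then shrinks, and it is zero when k equals ρ. This acts directly on PHQ-9 and less on BDI-II and SF-12.
- **Contrast.** The plan names no average over visits, so the Step 3 power figures are illustrative. Step 4 shows the same direction for the interaction test with equal SDs.
- **Sample size.** A reader might infer that the trial is underpowered. That is not shown: 70 per arm is exactly what a change-score analysis needs at ρ = 0.70 with equal SDs.
- **Responder model.** Response is already defined relative to baseline. Adding baseline scores to the logistic model turns the odds ratio into a conditional one and need not reduce its standard error.

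What remains is that the covariate is absent, the role of baseline is unstated, and baseline adjustment is never less precise in the four linear models.

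**Conclusion.** The point holds for the linear models of PHQ-9, BDI-II, PCS and MCS. The loss is one of precision: an unconstrained repeated-measures model remains valid under randomization, and nothing here implies bias or an inflated type I error.

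Its size depends on two quantities that the documents do not give, ρ and k, and on which reading applies. Over ρ of 0.3 to 0.7, the single-visit saving is 9 to 49% against follow-up only. Against change scores it is 35 to 15% with equal SDs, or about 22 to 2% at k = 0.8. For PHQ-9 on the likelier reading the gain could therefore be small. The follow-up-only reading, though less likely, has the more serious consequence, because its decisive test would not detect a constant treatment effect.

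**What to change.** By amendment before analysis, state whether baseline is a time level, and pre-specify one of the following for each continuous outcome, but not both:

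- (a) the 4-, 8- and 12-month values as responses, with the baseline score and its interaction with visit as covariates; or
- (b) baseline kept in the response vector, with the arm means constrained equal at baseline.

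In either case, test the treatment difference at each follow-up visit. Under (a) the time-by-treatment interaction alone must not be the test, since it misses a constant effect. State the covariance structure and the correlation behind the 70 per arm as well.

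Baseline adjustment of the logistic responder model is optional; if it is adopted, report the odds ratio as conditional.

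The cost is a few sentences in Section 5.6. No new data or patients are needed, so this is a free improvement.

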IIR03-315 Effectiveness and Implementation of Brief Cognitive Behavioral Therapy in
CBOCs

Funding Agency: Office of Research and Development

Principal Investigator: [name]

January 26, 2018

Abstract

Provide a summary of the study (recommended length: less than 500 words).

Depression is a serious health condition that places tremendous burden on patients and healthcare systems and is especially prevalent among Veterans. The delivery of complex evidence-based psychotherapy depression care is challenging, especially in settings such as primary care and community-based clinics. Within the Veterans Health Administration (VHA), efforts are needed to assist community-based outpatient clinic (CBOC) clinicians to deliver evidence-based psychotherapy for depression. The proposed 4-year multi-site trial seeks to train and assist (facilitate) CBOC clinicians in the use of a brief cognitive behavioral therapy (bCBT) and to subsequently monitor the effectiveness of this treatment on Veteran outcomes using a direct-referral versus enhanced usual care patient randomized trial design. Aim 1 will develop a series of strategies to train and assist CBOC clinicians in the use of bCBT at 16 CBOC sites connected to the Houston and Oklahoma City VA Medical Centers. Initial development of these strategies will involve CBOC clinician feedback in an iterative fashion that refines and enhances the training and support offered. Collectively, the development and assessment of these strategies will occur through a formal “formative evaluation” process. Formative evaluation will include a needs assessment as well as modifications to the clinical (bCBT) and implementation (clinician training and support) approaches. Following Aim 1, Aim 2 will seek to determine whether depression outcomes for Veterans differ as a function of the intervention (direct referral to bCBT provided by CBOC clinicians vs. enhanced usual care) at post-treatment (4-month), and 8- and 12-month follow-up. A total of 232 Veterans with clinically elevated symptoms of depression will be recruited from CBOC clinics associated with the Houston and Oklahoma City VA medical centers (8 CBOCs per station). Eligible Veterans will be randomized to either 1) a direct referral to a CBOC bCBT trained VA provider or 2) an Enhanced Usual Care (EUC) arm where participants will receive depression information and a depression tool kit as well as a note placed in their electronic medical record. EUC participants will be asked to talk to their primary care provider about additional depression treatment options. No participants in either the bCBT or EUC groups will be restricted in any way from the receipt of VHA services. Rather, the study will use VHA databases and chart review procedures to document and control for health care use during the study period.

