Unequal numbers of patients per group offers the advantage of reduction in unnecessary recruitment. We will have 80% power to detect a clinically important difference in means on the PHQ-9 between the intervention and usual care groups that is as small as 1.83, based on a small effect size of .30 and estimates of the pooled standard deviation of 6.1.⁵⁸ Lowe concluded that differences in PHQ-9 scores of 5 or greater reflect a clinically relevant difference. Similarly, we can detect differences in the means of the BDI between the treatment and EUC arms as small as 3.6 units, assuming a standard deviation of approximately 12 as seen in [name] et al. 2008.³¹ Assuming mean baseline BDI values of 20 or higher,³¹ we will have more than 80% power to detect a 50% reduction in BDI. For quality of life as measured by SF-12, a difference of one-half standard deviation (i.e., 5 points) is considered clinically significant.⁴⁸ On the basis of the standard deviation of the Mental Component Summary score (MCS) from [name] et al.³¹ of 14.7 and from Hendrick et al of 11.5, we will have 80% power to detect a difference in MCS scores as small as 3.45. For the SF-12 Physical Component Summary score, assuming standard deviations of 11 and 12 we can detect a difference in means as small as 3.3 points. Therefore, we will have more than 80% power to find clinically significant differences in quality of life.

Patient Availability: CBOCs in Houston and Oklahoma City care for a large (n = 50,000+) and diverse Veteran population. We estimate a sample of 7,500 assuming a 15% rate of elevated depressive symptoms.

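### The intention-to-treat models for Aim 2 adjust for treatment modality, which only bCBT patients who start treatment have, and for co-treatment not limited to baseline; the responder model is clearly exposed, the linear models only under some codings

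*Combined protocol and SAP*

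**What the plan says.** The Aim 2 paragraph of Section 5.6 states: "All analyses will be done on an intention-to-treat basis". It undertakes not to test baseline differences or to "adjust subsequent analyses for any variables we did not decide a priori to include in the regression models". It then specifies a longitudinal mixed model with treatment, time and their interaction, introduced with the words "To compare changes between the 2 groups over time". Separate models are planned for PHQ-9, BDI, SF-12 PCS and SF-12 MCS, and "logistic regression will be used for the combined depression outcome", that is, a 50% reduction on both depression scales.

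On covariates the plan says: "We will include the use of antidepressant medications, receipt of outpatient mental health care, the modality of treatment (e.g., telephone, in-person, combination", followed by site. The stated purpose is to control for differences between the arms. On the test it says: "The interaction between time and treatment will indicate whether there is a difference over time between the 2 groups".

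Other sections fix the timing of these covariates:
- Section 5.1 (Arm #1) has the bCBT patient and clinician agree on telephone, face-to-face or mixed sessions after assignment.
- Section 5.3 (Qualitative Interview) expects some bCBT patients to complete no session.
- Section 5.5 evaluates antidepressants in both arms at every assessment and monitors outpatient mental health care for use as a covariate.
- The Abstract says that databases and chart review will be used "to document and control for health care use during the study period".

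No section gives the coding of modality, restricts the other two covariates to baseline, or plans a model without them.

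**The concern.** Aim 2 asks what referral to bCBT does compared with EUC, with everyone analysed as randomised. A covariate that arises after assignment, and exists in one arm only, can change what the treatment term estimates. Choosing covariates in advance fixes which variables enter. It does not make them pre-randomisation, and it does not say how they enter.

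Modality is the main problem, because the 94 EUC patients (94/232 = 40.5%) have none. Depending on the coding, the treatment term may still estimate the effect of referral, may compare bCBT patients who never started with EUC, or may not be estimable. Antidepressant use and outpatient care raise a milder, conditional issue: if follow-up values are used and assignment changes them, part of the referral effect is adjusted away or distorted.

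**Working it through.** **Inputs from Section 5.6.** 138 bCBT and 94 EUC; effect size 0.30; SD 6.1; 25% attrition; therapist correlation 0.10 with 5.8 patients per therapist. The plan's figures reproduce: 0.30 × 6.1 = 1.83, as stated ("as small as 1.83, based on a small effect size of .30 and estimates of the pooled standard deviation of 6.1"); 1 + (5.8 − 1) × 0.10 = 1.48; 70 × 1.48 = 103.6, or 104. The calculations for a single follow-up time use 104 and 70 completers.

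**Assumptions not in the documents.** EUC response 15%; overall bCBT response 30%; no-session share 10–30% of bCBT; within-patient correlation 0.5; random dropout; the co-treatment rates below.

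**1. Responder model.** Response is defined relative to baseline, so there is no informative baseline value, and a benefit that is constant over months 4–12 sits in the treatment term. Take intercept, arm and three modality indicators, with EUC and no-session patients coded 'none'. The log-odds are b0 for EUC and b0 + bA for bCBT non-starters; starters add a modality term. So exp(bA) = [p/(1 − p)] / [0.15/0.85], where p is the response among non-starters:

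| p | Odds ratio by formula | Simulated, 104 vs 70 |
|---|---|---|
| 10% | 0.63 | 0.54–0.61 |
| 15% | 1.00 | 0.86–0.98 |
| 20% | 1.42 | 1.36–1.44 |
| 25% | 1.89 | 1.87–1.94 |
| 30% | 2.43 | 2.45–2.46 |
| 35% | 3.05 | not run |

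The referral odds ratio is (0.30/0.70)/(0.15/0.85) = 2.43 (simulated 2.4–2.5 without modality). Modality centred within bCBT gives 1.9–2.4.

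Simulated detection is 62–65% without modality. It is 24–40% under 'none' coding even when non-starters respond like everyone else (30%), and 38–60% with centring. These percentages ignore therapist clustering. As a rough guide, the variance of the log odds ratio is 1/(104 × 0.21) + 1/(70 × 0.1275) = 0.158, which gives about 61% power. Dividing 104 by 1.48 raises the variance to about 0.180 and lowers power to about 55%.

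**2. Estimability.** If every bCBT patient starts, the three modality indicators sum to the arm indicator. The five columns then have rank 4, and the arm effect is not estimable.

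**3. Linear PHQ-9 model, true effect −1.83, month-4 term.** A patient-level modality term shifts baseline and follow-up equally, so it cancels from the change. The interaction is −1.80 to −1.87 without modality. It is the same with modality as a patient-level main effect, or by visit but centred within bCBT. It changes under two other set-ups with EUC coded 'none':

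| Non-starters minus EUC | Modality by visit | Follow-ups only (treatment term) |
|---|---|---|
| +1.83 | +1.8 to +1.9 | +1.8 to +1.9 |
| 0 | about 0 | 0.0 to −0.1 |
| −1 | −1.0 | −0.9 to −1.1 |
| −1.83 | −1.8 to −1.9 | −1.8 to −1.9 |
| −3 | −3.0 | −3.0 |

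Standard errors are 1.01–1.40 against 0.84 (by visit) and 1.10–1.65 against 0.85 (follow-ups only).

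**4. Co-treatment, total referral effect −1.83.** There is no bias if use is equal (40% in each arm), if use is unrelated to outcome, or if it enters as a patient-level main effect with baseline as an outcome time. With use of 30% against 50%, in either direction, the estimate is −1.3 to −2.4 by visit and −1.1 to −2.6 with follow-ups only. If use is both driven by severity and effective, the biases partly cancel (−1.6 to −2.1 and −1.7 to −1.9).

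**The case against.** A reader might infer that no Aim 2 result, the PHQ-9 included, could be read as the effect of referral. The documents do not support that. A combination category most naturally summarises a whole course of treatment. The course is planned to last at most four months, so modality has no obvious value at months 8 and 12. The plan speaks of comparing changes, and Table 3 schedules the outcome scales at baseline. All this favours a patient-level term with baseline as an outcome time, under which the named interaction is intact. That stands; the text still does not settle it.

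The exposed responder outcome is also not the one behind the power calculation, which concerns mean differences. And the named time-by-treatment test says little there in any case: in a repeated responder model it rejected 3–7% of the time with or without modality. That is a separate weakness, not caused by modality. Both points narrow the reach of the problem. They do not repair the responder model's treatment term.

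Controlling for co-treatment is a declared aim: Sections 5.1 and 5.5 refer to confounding by concurrent treatment and to encounters outside the study. Nor do the documents show that use will differ by arm. The chart note records encouragement to seek services in both arms, and Section 5.5 raises an effect of assignment on medication only as a question. So this part stays conditional.

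Finally, the response rates and no-session shares are assumed, so the figures show what is possible, not an expected size.

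**Conclusion.** The point holds and should be settled before analysis. The intention-to-treat statement and the covariate list do not fit together for modality. In the responder model under 'none' coding, the treatment term is not the referral effect: a true odds ratio of 2.43 could appear as anything from 0.63 to 3.05, depending on how non-starters fare, and precision falls even without selection. Coding centred within bCBT does much less harm. The change of comparison and the loss of rank are algebraic; the sizes rest on the assumed response rates.

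For the four linear outcomes the interaction is preserved if baseline is an outcome time and modality is a patient-level term, or if modality is centred within bCBT. It becomes non-starters against EUC only if modality enters by visit with EUC as 'none'; the same happens to the treatment term if only follow-ups are modelled. Co-treatment adjustment biases the referral effect only when follow-up values are used, use differs by arm and use is related to outcome. The detection percentages are illustrative only.

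**What to change.** In Section 5.6:
- Limit the main Aim 2 models to arm, time, arm-by-time, site and pre-randomisation covariates.
- Take antidepressant use and outpatient mental health care over a stated pre-baseline window, for example the 12 months already used for the Charlson index.
- Analyse modality within bCBT only, where Sections 5.1 and 5.5 already plan to examine it.
- Report post-baseline antidepressant use and outside mental health care by arm. Label any model that adjusts for them secondary or exploratory, and state its coding in advance.
- State that baseline is an outcome time in the linear models.
- Document the change as made before outcomes by arm are seen. This matters because the protocol is dated January 2018 and enrolment was expected from March 2015.

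The cost is wording plus a baseline look-back in the planned extraction, because Table 3 shows medication and service-use extraction only in the 12-month column. Medication start dates and a 12-month pre-baseline extraction for the Charlson index are already planned. N stays 232 and the detectable PHQ-9 difference stays 1.83.
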